3. APPROACH

The overall design proposed for this research is a sequential integrated mixed methods study (109, 110). The study will consist of three phases, one for each specific aim, each of which informs and supports the next: (1) a qualitative formative phase to refine intervention design; (2) a randomized controlled trial to assess the feasibility of collecting weight management-related PGHD and PROs data through COTS health IT solutions; and (3) the creation of a data model, ontology mapping tool and set of FHIR resources to support integration of PGHD and PROs data into clinical information systems.

3.1. Setting

This study will be conducted at Denver Health (DH), an urban integrated safety net health delivery system that serves as the primary health care safety net for the city and county of Denver, Colorado. DH serves an estimated one in four Denver residents, or approximately 190,000 individuals per year. Almost two-thirds of the patients seen are members of racial/ethnic minority groups. The majority of DH patients are low-income, with over 70% living beneath the poverty line, and over 95% living within 200% of the federal poverty level. DH includes a 525-bed acute care hospital with an academic Level 1 Adult and Pediatric Level II Trauma Center, nine federally qualified community health centers, sixteen school-based clinics in the Denver public school system, a 100-bed non-medical detoxification facility, correctional care services for Denver's jails, a health maintenance organization, the 911 medical response system, a 24-hour nurse line, the Rocky Mountain Poison and Drug Center, and the Denver Public Health department.

3.3. Preliminary Studies

For the last six years, our research team has collaborated on projects designed to improve health care quality and delivery for disadvantaged populations through health IT solutions. Common research themes among the projects described include 1) using qualitative methods to elicit patients' perspectives about employing specific familiar technologies, 2) creating and/or enhancing data infrastructure, and 3) patient-generated data collection through text messaging. The proposed work will build on this foundation by engaging disadvantaged patients in the use of COTS health IT solutions that are more advanced, feature-rich, and secure than text messaging alone. It will also enhance patient-reported data collection by including not only PGHD but also more complex data elements, such as multi-question validated PROM instruments and patient contextual data, and will define a route to integrating these discrete data elements into interoperable EHRs, clinical information systems, and big data infrastructures. Brief descriptions of pertinent studies are included below.

3.3.1. Chronic care and patient relationship management proof of concept (internal funding)(77).

This mixed methods proof of concept study involved the creation of a health IT system to support chronic disease management through bidirectional text messaging. Adult patients with diabetes self-reported fasting glucose levels on a daily basis in response to a text message prompt; a nurse case manager reached out to follow up by phone with patients whose glucose levels were outside an accepted clinical range. Patients also

received text message reminders of upcoming appointments in an urban safety net health care system. Patients responded to 68% of prompts and reported feeling more connected to the health system.

3.3.2. *Expanding comparative effectiveness research (CER) capability through complex patient relationship management. AHRQ, grant 1R24HS019453.* (79, 111)

This mixed methods feasibility study built on the previous proof of concept to demonstrate the use of an expanded health IT infrastructure for patient-reported data collection and subsequent data integration into an EHR. Adult patients with diabetes used a text message-based mobile health infrastructure to report fasting blood glucose levels, blood pressure measurements, and/or step counts in response to regularly-scheduled prompts. Reported values were automatically formatted into a self-reported data log, transmitted to the EHR, and made available to providers through attachment to the patient's medical record as an image file.

3.3.3. *Integrated model of individualized ambulatory care for low-income children and adults (21st Century Care). CMMI, Health Care Innovation Award 1C1CMS331064.* (112, 113)

This program sought to improve outcomes associated with the Triple Aim (114) through an integrated approach combining revised staffing models, updated approaches to team-based care, and the use of health IT infrastructure tailored to support care management, complex data reporting and analysis, and between-visit text message outreach initiatives. As part of the project, the RE-AIM framework (115) was used to assess (a) pilot and expansion-phase process and health outcomes for each of 5 separate text messaging initiatives targeted at improving service delivery and health promotion, and (b) the implementation and adoption of new health IT infrastructure to improve care coordination and management for safety net patients across 8 primary care clinic settings.

3.3.4. *Developing infrastructure for patient-centered outcomes research (PCOR) at Denver Health. AHRQ, grant 1R24HS022143-01.* (116)

This project created multiple PCOR infrastructure components at Denver Health: a research support core, a new investigator training program, a community advisory panel, and three research projects. The first research project was a randomized controlled trial to examine the use of text messaging for weight loss support among patients with pre-diabetes, which resulted in clinically significant weight loss. Another pertinent component of the overall grant-funded initiative involved the expansion of an existing virtual data warehouse (VDW) to incorporate mental health data from two partnering health for public health surveillance and PCOR purposes.

3.4. Study Design and Methods

3.4.1. *To assess the needs and preferences of disadvantaged patients and safety net health care providers regarding the use of health IT for communicating PGHD and PRO.*

Design. Semi-structured interviews with providers and focus groups with patients will be conducted in the qualitative formative phase of this proposed study. These sessions will elicit in-depth information that is expected to yield a rich contextual understanding of needs and preferences for COTS health IT-based PGHD and PROs reporting, including perceived self-efficacy at doing so and an assessment of gaps in current systems.

Settings/ populations. Provider interview participants will be identified from among the 1,087 credentialed providers employed by and affiliated with DH. Patient focus group participants will be recruited from the 9 federally qualified health centers (FQHCs) that provide primary care services to DH patients.

Methods. Semi-structured protocols will be developed for use in both interviews and focus groups. Protocols will be tailored to elicit factor data that can be used in qualitative comparative analysis (QCA). QCA is a case-oriented approach based on set theory and Boolean algebra, and uses configurational methods to evaluate complex causal relationships and factors deemed necessary and sufficient to influence outcomes (117, 118). Unlike regression models, QCA assumes multiple paths lead to intended goals ("equifinality"), and explicitly assesses the effect of combinations of factors ("multiple conjunctural causation") (117-119). QCA has been used to study health care models and practices as well as structures and processes linked to weight loss outcomes (118-120). Questions anticipated to elicit QCA factor data include inquiries about user-preferred

technologies, willingness and ability to use technology to support weight loss, and social and behavioral factors affecting both weight loss and technology use. Protocol questions will also be informed by previous findings from a consumer health informatics-focused survey of DH patients (81) and by qualitative evaluations conducted during the preliminary studies (Section 3.3), and will address health IT design considerations of usefulness, usability and user experience, and care process impact. A draft protocol is included as Appendix 1. Purposeful sampling (121) will be used to enroll overweight and obese adult patients (BMI 25.0-39.9, 18+ years) in focus groups stratified by two domains: primary language (English or Spanish) and self-reported technology use (high or low). Focus groups will be conducted by a trained facilitator in English or Spanish based on patients' primary language, with the assistance of a bilingual research assistant trained in qualitative methods as an observing note-taker. Patients will be classified as technology users based on their responses at enrollment to screening questions about IT use type and frequency. In order to reach saturation, defined as the point at which no new topics and themes emerge from discussion, 2 focus groups will be conducted for each domain, for a total of 8 groups. Six to 8 patients will be recruited per group, for a total of 48 to 64 patients. Provider interview participants will be solicited as key informants identified by their peers as those who are likely to be particularly knowledgeable about the topic of interest (121). Both patient and provider participants will receive a \$25 gift card incentive. Two to 3 interviews are anticipated per FQHC site, for a total of 18 to 27 interviews. All focus group and interview sessions will be audio recorded and transcribed; additional observations will be documented through detailed note-taking.

Data Analysis. Transcript and note data will be subjected to content analysis. A list of codes will be developed *a priori*, with additional codes added through a heuristic approach, which supports the incorporation of emergent topics and themes. Data will be independently coded in Atlas.ti by both the focus group facilitator/interviewer and the observing note-taker, with interrater reliability assessed through the kappa statistic (122-124). Identified patterns will be incorporated into an overall synthesis that will be used to inform the development of the intervention and to create set-theoretic groups for QCA (see Specific Aim 2). Results are anticipated to reveal commonalities about the types of technology that patients use; data types, frequencies and methods for reporting data as preferred by both patients and providers; and contextual factors that affect technology use and weight loss (economic, educational, geographic, social, and behavioral). These will be used to refine the list of specific PGHD and patient contextual data elements for patients to report.

3.4.2. Specific Aim 2: To demonstrate the feasibility of PGHD and PRO collection through COTS health IT solutions through a patient-centered pilot intervention for weight management among disadvantaged patients.

Design. This phase of the study will be conducted as a randomized controlled trial (RCT).

Settings/ populations. Intervention and control patients for this trial will be recruited from among DH overweight and obese adults (BMI 25.0-39.9, 18+ years) who are considered to be at medium health risk according to a risk stratification algorithm developed by DH and used in its 21st Century Care model to tailor care to patients according to level of need (125, 126). Risk stratification is based on a combination of clinical criteria, a patient's diagnostic score (127), and health care utilization (127, 128). Previous findings indicate an association between good general health status on the CDC's Healthy Days measure (HRQOL-4) and the use of health information among patients in the medium risk group. This association was absent among patients in the lower risk group and thus may indicate a point in chronic disease progression when health IT-based interventions could positively affect chronic disease management through patient engagement, with the long-term goal of delaying or avoiding poor health outcomes (81).

Methods. Recruited participants will be randomized to one of two arms, intervention or control. Both intervention and control groups will engage in a 16-week program where they will receive regular health promotion messaging about (a) food, nutrition, and diet; and (b) exercise and physical activity. Existing content in these topic areas is available in a DH text messaging library aligned with the Centers for Disease Control and Prevention's (CDC) evidence-based Diabetes Prevention Program (80), for which a previous study demonstrated clinical efficacy (116). Additional messaging content will be informed by focus group and interview findings. Intervention patients will be asked to track PGHD elements related to weight management through a mobile health app loaded on their phones and/or through using a fitness tracker, depending on patient preference, and to share that information with the research team. If intervention patients do not have a fitness tracker, a low-cost COTS option will be provided for them. Both iOS and Android phone options will be

supported. The app will be selected from a limited set of well-established options such as LoseIt!, MyFitnessPal, Apple Health, or Google Fit. The PGHD requested through active tracking and patient data entry will include self-monitoring elements previously shown to be successful at encouraging obesity-related behavioral change (129), such as calorie intake, food logging, minutes of physical activity, and weight. Patient contextual data requested through passive tracking may include items such as geographic location, sleep quality, and heart rate. Any additional data requested will be determined based on the results of Aim 1 and in consultation with the research team to identify social, behavioral, and clinically relevant information. Both intervention and control patients will be weighed on a clinic scale and asked to complete three PROMs pre- and post-intervention. These include the short form of the Patient Activation Measure (PAM-13), which is a validated PROM that assesses an individual's knowledge, skills and confidence in self-management behaviors (35, 36); the HRQOL-4, which is a validated PROM that assesses patients' overall physical and mental health status over the prior 30 days (37); and the Healthy Days Symptoms Module, which is a validated PROM that assesses physical and mental health symptoms which may have affected patients' lives over the prior 30 days (37). Intervention patients will also be asked to complete the three PROMs once each per month over the course of the 16-week intervention by email, online web form, text message, or app-based private message. Only privately submitted PROM data will be used in analysis, to protect patient privacy and to avoid social desirability bias due to self-curation behaviors associated with public reporting. One PROM will be collected per week, to avoid overburdening patients while ensuring a monthly collection of PROM data. The fourth week will include a simple check-in request, to maintain the weekly communication pattern. PGHD and PROs data will be extracted from shared systems, online forms, and messages as appropriate and placed into a REDCap (130) research database created for the project. These data will also be made available to and actionable by DH providers monthly through manual transfer to practice-standard patient-reported data forms and subsequent entry into the EHR. As this is a feasibility study, automated data exchange is beyond the scope of this initial project; however, the product of Specific Aim 3 will support future automated integration.

Outcomes and measures. The primary outcome of interest for the RCT is *patient engagement*. This outcome will be measured by patient response rates to data requests; by the frequency of unprompted messages sent by patients to research personnel; and by performance on the PAM-13. Secondary outcomes include weight loss and performance on the HRQOL-4 and Healthy Days Symptoms PROMs pre- and post-intervention. Weight loss will be assessed as change in body mass index (BMI) and absolute percent weight.

Data Analysis. Descriptive statistics will be computed for participant demographic characteristics (e.g., age, gender, race/ethnicity). Group differences (intervention vs. control) will be evaluated to ensure that the random group assignments were similar. If statistically significant differences ($p < 0.05$) are found between the groups for demographic or baseline measures, these will be controlled for in subsequent analyses. Logistic regression or the Chi-square test of proportions will be used to test differences in response rates and PROM scores between the RCT intervention and control groups. The distribution of the number of unprompted messages will be assessed and either analyzed using Poisson regression or dichotomized based on a clinically relevant cut-off and analyzed with either logistic regression or the Chi-square test of Proportions. Weight loss will be analyzed using the most appropriate and parsimonious multivariable regression technique, based on the nature of the outcome variable (e.g., continuous, time-varying, dichotomous, etc.). Fuzzy-set QCA will be conducted to examine the impact of factors identified through work conducted under Specific Aim 1.

Power. A total sample size of 256 patients is necessary to detect a proportional difference of 20% (0.55 intervention; 0.40 control) in the primary outcome between the intervention and control groups with 90% power ($\alpha = 0.05$). A sample size of 192 patients would be needed at 80% power. Given the nature of this feasibility study, we will attempt to recruit 300 patients for the RCT, but will consider the study adequately powered with 200 patients enrolled (100 intervention, 100 control). This also allows for some loss to follow-up.

3.4.3. Specific Aim 3. To create an ontology mapping and set of interoperability resources which can be used to support integration of PGHD and PROs into clinical information systems.

Design. In this phase of the study, an enhanced entity-relationship (EER) data model will be created for the common set of PGHD elements and PROMs identified and collected in Aim 2. Knowledge representation techniques will be utilized to describe the model in ontological terms, and concepts from the UMLS Metathesaurus will be used to create a mapping to the SNOMED-CT clinical vocabulary. The model will be used to create a set of FHIR resources which can be used for future implementation to facilitate interoperable data

transfer between FHIR-compliant mobile health IT solutions, EHRs and other FHIR-compliant clinical information systems.

Methods. The PGHD elements and PROMs used in Aim 2 will be reviewed for confirmed feasibility and used to establish a final, feasible set list of feasible data elements that are perceived to be valuable to patients and providers engaged in obesity-related chronic disease management. Each data element will be documented as a FHIR resource and represented in the XML format. An assessment of data exchange and common technical interface requirements will be conducted for the COTS solutions used by patients in Aim 2 (e.g., MyFitnessPal on iOS and Android, integrated with a fitness tracker and/or mobile phone as a passive data collection source). The results of this assessment will be documented as a FHIR interface description and profile. Relationships between model elements will be portrayed using common knowledge representation techniques. An “inside-out” design will be used for three-phase model development, including classification, in which similar data elements are grouped into entity types; identification, in which types are assigned unique identifiers; and relationship identification. Relationship identification is a four-part approach that includes specialization, in which too-general types are refined; generalization, in which too-specific types are abstracted; aggregation, in which composite objects are created; and association, in which objects from independent types are linked (131, 132). The knowledge representation process will incorporate inferential reasoning and the creation of correspondence between model concepts (entities and attributes) and their real-world analogues (132, 133). Once the model is developed, a formal syntactic description will be created by mapping meaning-equivalent concepts in the UMLS Metathesaurus to the SNOMED-CT clinical vocabulary (134-136). This description serves as an ontology, utilizing Guarino’s expansion on Gruber’s definition of an ontology as “a specification of a conceptualization” to include a language-dependent set of relations (the vocabulary-mapped model) defined on a particular domain space (the patient-reported data elements) (137, 138). Should model elements be defined that have no direct mapping, the closest equivalent will be identified and an update will be proposed for the next SNOMED-CT release.

Results. The detailed EER model schema, data exchange and interface assessment, ontology mapping, and comprehensive list of UMLS concepts and SNOMED CT terms used in the ontology mapping are the expected products of this aim. The data model schema and ontology mapping will be documented as FHIR resources. The term “resource” is used to refer to all exchangeable content, and each FHIR resource includes: 1) common definitions and representations based on data types with reusable patterns; 2) a common metadata set; and 3) a human-readable part to aid user interpretation. FHIR also includes an interface description and a profile for each implementation. The data exchange and interface assessment will be used to create the FHIR interface description and profile. All FHIR resources created will be packaged as an extensible set which can subsequently be used for integration of PGHD and PROs into interoperable EHRs, clinical information systems, and big data infrastructures.

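### The RCT does not state that baseline technology use or patients' own app and tracker use will be recorded in both arms, and it adjusts only for measures that happen to differ at p < 0.05

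*Combined protocol and SAP*

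**What the plan says.** **Aim 1 (section 3.4.1).** The patient sessions are "focus groups stratified by two domains: primary language (English or Spanish) and self-reported technology use (high or low"). Technology use is measured: "Patients will be classified as technology users based on their responses at enrollment to screening questions about IT use type and frequency". Aim 1 also looks more widely, at "contextual factors that affect technology use and weight loss (economic, educational, geographic, social, and behavioral").

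**RCT allocation (section 3.4.2, Methods).** "Recruited participants will be randomized to one of two arms, intervention or control". No allocation method or stratification factor is given.

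**RCT data.** Both arms are weighed in clinic and complete three PROMs before and after the program. Prior ownership of a device comes up for one arm only: "If intervention patients do not have a fitness tracker, a low-cost COTS option will be provided for them". No item on controls' own apps or trackers is mentioned.

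**RCT analysis (section 3.4.2, Data Analysis).** "Descriptive statistics will be computed for participant demographic characteristics (e.g., age, gender, race/ethnicity"). If differences at p < 0.05 "are found between the groups for demographic or baseline measures, these will be controlled for in subsequent analyses". Aim 1 factors return separately: "Fuzzy-set QCA will be conducted to examine the impact of factors identified through work conducted under Specific Aim 1".

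**The concern.** The primary outcome is engagement, measured by response rates to data requests, unprompted messages and the PAM-13. Section 1.4 rests the study on the Technology Acceptance Model, under which ease and familiarity with a technology raise the likelihood of reporting. On that reasoning, baseline technology use should predict the outcome. A strong predictor that is not prespecified as a covariate costs precision, and a chance imbalance in it goes uncorrected unless it is large enough to reach p < 0.05.

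The second issue is the contrast between arms. The candidate apps are public products, and the protocol describes such technologies as widely adopted in this population. Some controls may already log weight, food or activity. If nobody records this, a small difference in PAM-13 or weight could reflect either a weak intervention or a small difference in what the two arms did.

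**Working it through.** **1. The plan's own figures.** The Power paragraph gives 256 patients (90% power) and 192 (80%), α = 0.05, for a difference described as 20% but printed as 0.55 vs 0.40. Per arm, two-sided with pooled variance:

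n = [1.96·√(2p̄(1−p̄)) + z_β·√(p₁(1−p₁)+p₂(1−p₂))]² / (p₁−p₂)²

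- 0.55 vs 0.40, 90%: (1.96·0.7062 + 1.2816·0.6982)² / 0.0225 = 230.8, so 231 per arm, 462 in total. At 80% the total is 346.
- 0.55 vs 0.35, 90%: (1.96·0.7036 + 1.2816·0.6892)² / 0.04 = 127.9, so 128 per arm, 256 in total. At 80% the total is 192.

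The printed rates do not reproduce the stated sizes; a true 20-point difference does. That is a separate matter, but it means both pairs of rates must be carried below. At 200 patients the normal approximation gives power of 57% (0.55 vs 0.40) and 82% (0.55 vs 0.35).

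**2. What adjustment gains.** Assumptions not in the documents: half the patients are high technology users, and response rates differ between high and low users by the gap shown, equally in both arms. Setting: 100 per arm (the plan's minimum), simple allocation, two-sided 0.05. Simulated power, unadjusted chi-square against a test stratified by technology use (Cochran-Mantel-Haenszel), good to about one point:

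| Gap, high vs low users | 0.55 vs 0.40, adjusted | 0.55 vs 0.35, adjusted |
|---|---|---|
| 10 points | 57% | 82% |
| 20 points | 59% | 83% |
| 30 points | 61% | 85% |
| 40 points | 64% | 88% |
| 50 points | 69% | 91% |
| *Unadjusted, any gap* | *58-59%* | *83%* |

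The unadjusted values sit a point or two above the normal approximation in step 1.

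**3. What the p < 0.05 rule recovers.** At 0.55 vs 0.35 and a 40-point gap, power is 83% unadjusted, 83% under the plan's rule (supposing technology use is collected) and 88% when always adjusted. The rule seldom acts.

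**4. Chance imbalance.** The standard error of the difference in the proportion of high users is √(2·0.5·0.5/n).

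- n = 100: 0.0707. P(imbalance above 10 points) = P(|Z| > 1.41) = 16%. The rule triggers at 1.96·0.0707 = 13.9 points.
- n = 150 (target of 300): 0.0577. P(|Z| > 1.73) = 8%. The rule triggers at 11.3 points.

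A 10-point imbalance with a 40-point gap moves the observed difference by 0.10·0.40 = 4 points in either direction, and in neither case would the rule correct it.

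**5. Stratified randomisation.** At 0.55 vs 0.35, adding it to adjustment takes power from 85.1% to 85.5%, 87.9% to 88.3% and 91.4% to 91.6% for gaps of 30, 40 and 50 points: under half a point each time.

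**6. Self-tracking controls.** If a fraction c of controls behaved fully like intervention patients, a mean difference Δ would shrink to (1−c)Δ: 90%, 80% or 70% of Δ for c = 10%, 20% or 30%. This is an upper bound on dilution, because the intervention also includes sharing data with the team, monthly PROMs and reporting to providers. No value of c is given in the documents.

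**The case against.** The strongest reply is that simple randomisation in a feasibility study is acceptable and unbiased, and that the documents are silent on this point rather than contrary. Much of that stands, and several stronger readings should be resisted.

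- *Language and technology use are the two factors that matter.* They are sampling strata for focus groups; Aim 1 lists several other kinds of factor. Nor do the documents say that the RCT enrols Spanish speakers.
- *Technology use will never be available, or never adjusted for.* The demographics are given as examples, further data may be added after Aim 1, and the conditional rule covers any baseline measure that was collected. The planned QCA is case-oriented and so would seem to need such factors on trial patients, though the text does not say when or in which arm. QCA is not, however, adjustment of the arm comparison.
- *The trial is biased without strata.* Chance imbalance averages out over randomisations. The cost is precision.
- *A null result could not be interpreted.* Randomisation balances prior self-trackers in expectation. Owning a tracker does not obviously raise a control's response to study requests, so dilution bears mainly on PAM-13 and weight.

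It is also fair to object that no document quantifies how prognostic technology use is. At gaps of 10 to 20 points adjustment gains nothing. The text between sections 3.1 and 3.3 was not available for this review.

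What remains is that the plan states no measurement in both arms and no prespecified covariate, and its conditional rule is a poor substitute.

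**Conclusion.** The point holds in a limited form. Section 3.4.2 does not commit to recording baseline technology use, or own app and tracker use, in both arms, and its adjustment rule recovers almost none of the available precision. At the minimum of 200 patients with half high users, prespecified adjustment is worth about 2 to 11 points of power for response gaps of 30 to 50 points across the two pairs of rates. It is worth nothing at 10 to 20 points, with a loss of about a point at 10. The benefit therefore depends on technology use being strongly prognostic, which the protocol's theory suggests but no figure supports. The case for recording self-tracking does not depend on that gap: without it, the achieved contrast behind the PAM-13 and weight results is unknown. The change is worth making because it is cheap and because baseline status cannot be reliably recovered after randomisation.

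**What to change.** 1. Before randomisation, give every RCT patient the Aim 1 technology-use screening questions and one item on whether they now log weight, food or activity in an app or tracker. Repeat that item at week 16 in both arms.
2. Name technology use as a covariate in all between-arm models, whatever any baseline test shows. Add primary language if Spanish speakers are enrolled. For proportions use logistic regression or a Mantel-Haenszel analysis, since the plain chi-square test that the plan also allows cannot carry covariates. Drop the p < 0.05 rule for choosing these covariates.
3. Report self-tracking by arm at baseline and week 16 as the achieved contrast, and read the PAM-13 and weight results beside it.
4. Stratified randomisation may be added but is not needed.

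Cost: questions already planned for Aim 1, about two minutes per enrolment, a few lines of analysis text, and a negligible loss of power if the factor proves weak. The sample size does not change on this account.
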